5.1 Study Endpoints

5.1.1 Primary Endpoints

For Cohort 1, the primary endpoint is RD of lenvatinib based on the TiTE-CRM design. While for Cohort 3A, it is RD of the combination treatment (lenvatinib + etoposide + ifosfamide).

For the three Phase 2 cohorts, the primary endpoints are:

- Cohort 2A (DTC): ORR, ie, the proportion of subjects who have a BOR of complete response (CR) or partial response (PR) for subjects with measurable disease and BOR for all subjects based on RECIST 1.1
- Cohort 2B (Osteosarcoma): PFS-4, ie, the percentage of subjects evaluable for PFS-4 who are alive and without PD at 4 months from the first dose based on RECIST 1.1. Subjects evaluable for PFS-4 includes those treated at least 4 months or those who died or radiologically progressed within 4 months after first dose.
- Cohort 3B: PFS-4

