5.4.2.1 Primary Efficacy Analyses

COHORT 2A: DTC

The primary efficacy endpoint is ORR for subjects with measurable disease and BOR for all subjects. Tumor response will be based on RECIST 1.1 and assessed every 8 weeks. The analysis will be descriptively performed on the Full Analysis Set.

COHORT 2B: SINGLE-AGENT EXPANSION

The primary efficacy endpoint is the PFS-4 rate based on RECIST 1.1. This is the proportion of subjects free of progression at 4 months. The PFS-4 rate will be estimated using the binomial proportion and the corresponding 80% and 95% exact binomial distribution CIs ([Clopper and Pearson, 1934](#)) will also be provided. The PFS-4 rate will also be tested using a null hypothesis that the PFS-4 rate is $\leq 25\%$ tested against the alternative hypothesis of a PFS-4 rate $\geq 45\%$, using the 1-sample exact test of a single proportion, at the 1-sided 0.1 level. These analyses will be performed on the lenvatinib-naïve subjects in the Full Analysis Set and the Per Protocol Analysis Set.

The PFS-4 rate will be calculated using PFS-4 evaluable subjects. These are defined as follows.

PFS-4 evaluable subjects:

- includes subjects who were treated with study medication at least 16 weeks;
- includes subjects who died or radiologically progressed within 16 weeks after the first administration of study medication. These subjects are not considered free of progression at 4 months;
- includes subjects who received anticancer treatment within 16 weeks after the first administration of study medication. These subjects are not considered free of progression at 4 months;
- excludes those who discontinue the study due to AE or reasons other than disease progression, death, or receiving anticancer treatment within 16 weeks after the first administration of study medication;
- excludes subjects administered any study medication with no baseline or no postbaseline tumor assessments.

COHORT 3B: OSTEOSARCOMA COMBINATION EXPANSION

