The primary efficacy endpoint is the PFS-4 rate based on RECIST 1.1. This is the proportion of subjects free of progression free at 4 months. The PFS-4 rate will be estimated using the binomial proportion along with the corresponding exact binomial 80% and 95% CIs. The PFS-4 rate will be tested using a null hypothesis that PFS-4 rate is $\leq 25\%$ tested against the alternative hypothesis of a PFS-4 rate $\geq 50\%$, using the 1-sample exact test of a single proportion, at the 1-sided 0.1 level. This analysis will be performed on the lenvatinib-naïve subjects in Full Analysis Set and Per Protocol Analysis Set, while subjects enrolled from Cohorts 1 and 2B will be summarized only as appropriate.

The PFS-4 rate will be analyzed using PFS-4 evaluable subjects. These are defined as follows.

PFS-4 evaluable subjects:

- includes subjects who were treated with study medication at least 18 weeks
- includes subjects who died or radiologically progressed within 18 weeks after the first administration of study medication. These subjects are not considered free of progression at 4 months.
- includes subjects who received anticancer treatment within 18 weeks after the first administration of study medication. These subjects are not considered free of progression at 4 months.
- excludes those who discontinue the study due to AE or other reasons than disease progression, death , or receiving anticancer treatment within 18 weeks after the first administration of study medication
- excludes subjects administered any study medication but had no baseline or no postbaseline tumor assessments.

SURGICALLY REMOVED LESIONS

For Cohorts 2B, 3A and 3B, removal of existing (not new) osteosarcoma metastatic lesion(s) is permitted after the completion of the first 4 months of the treatment period without PD. The time points for tumor response assessment after tumor removal will be considered ‘Not Evaluable’ unless the tumor response is considered PD for the following reasons:

- appearance of an unequivocal new lesion
- unequivocal progression of non-target lesions or target lesions

Lesions removed before the first 4 months are permitted only in the case of PD.

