5.4.2.2 Secondary Efficacy Analyses

The secondary efficacy endpoints include BOR over the treatment period (except for Cohort 2A), ORR (except for Cohort 2A), DCR, and CBR, as well as DOR (measurable disease only). PFS and TTP are defined in SAP [Section 5.1](#) and will be performed for subjects in the Full Analysis and Per Protocol Analysis Sets.

Subjects who do not have a tumor response assessment for any reason will be considered nonresponders and will be included in the denominator when calculating the response rate. The count and percentage for ORR will be summarized by dose level for Cohorts 1 and 3A and by cohort for Cohorts 2B and 3B. ORR and corresponding 95% CI based on the exact binomial distribution will be estimated for all corresponding treatment cohorts.

The count and percentage for both the DCR and CBR will be summarized for each treatment cohort, along with the exact 95% CI for.

The median and quartiles of DOR will be estimated by the Kaplan-Meier (KM) method ([Kaplan and Meier, 1958](#)), and the 95% CI estimated with a generalized Brookmeyer and Crowley method ([Brookmeyer and Crowley, 1982](#)).

For PFS, if a subject has not experienced PD or death, then the subject's data will be censored on the date of the last adequate radiologic assessment.

TTP will be calculated using data from all subjects in the Full Analysis Set. The calculation for TTP does not classify deaths as events.

The PFS censoring rules in this SAP and definition of progression date follow the [Food and Drug Administration \(FDA\), Guidance for Industry Clinical Trial Endpoints for the Approval of Cancer Drugs and Biologics \(2007\)](#) (See SAP Table 3). The PFS censoring rules are referenced in SAP Table 3 and TTP censoring rules are referenced in SAP Table 4.

Table 3 Censoring Rules for Analysis of Progression-Free Survival

No	Situation	Date of Progression or Censoring	Outcome
1	No baseline tumor assessments	Date of first dose	Censored
2	No postbaseline tumor assessments	Date of first dose	Censored
3	Progression documented between scheduled visits	Date of first radiologic PD assessment	Progressed
4	More than 1 NE tumor timepoint assessment	Date of last adequate radiologic assessment before NE tumor assessments	Censored
5	No progression at time of data cutoff	Date of last adequate radiologic assessment	Censored
6	New anticancer treatment started	Date of last adequate radiologic assessment prior to or on date of new anticancer treatment	Censored

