7	Death before first tumor assessment	Date of death	Progressed
8	Death between adequate assessment visits*	Date of death	Progressed
9	Death or progression after more than one missed visit/tumor assessment**	Date of last adequate radiologic assessment before missed tumor assessments	Censored
10	Treatment discontinuation for reasons other than PD	Date of last radiologic assessment before treatment discontinuation	Censored

CR = complete response, NE = not evaluable, PD = progressive disease, PR = partial response, q6w = every 6 weeks, q8w = every 8 weeks, SD =stable disease.

* Adequate tumor assessment is radiologic assessment at regular interval as defined in the protocol.

** More than 1 missed visit/adequate tumor assessment is defined as having either 1 of the following 2 durations being longer than 18 weeks – 1 day, which is 125 days ($= ((8+1) \times 2 \times 7) - 1$) for subjects on the q8w tumor assessment schedule in Cohorts 1, 2A and 2B; while 14 weeks – 1 day, which is 97

days (= ((6+1) x 2 x 7) – 1) for subjects on the q6w tumor assessment schedule in Cohorts 3A and 3B:

- a. Duration between 2 consecutive tumor assessments
- b. Duration between the last adequate tumor assessment and death or PD

The priority of the censoring rules is as follows:

1. If the subject had PD or death, the following sequence will be applied:

- If a subject did not have a baseline or postbaseline tumor assessment (Nos. 1 and 2), the subject will be censored on the date of first dose. However, if the subject died within 125 days in Cohorts 1, 2A and 2B or 97 days in Cohorts 3A and 3B following the first dose and did not receive a new anticancer treatment, it will be counted as PFS event at the date of death. If a subject had new anticancer treatment before PD or death (No. 6), the subject will be censored on the date of the last adequate tumor assessment prior to or on the date of new anticancer treatment. If PD is reported after the drug discontinuation visit, the subject will be censored at the date of last radiologic assessment before drug discontinuation except when PD happened at the same visit as drug discontinuation (No. 10). If PD happened within 4 weeks of drug discontinuation (Week 16 for Cohort 2 and Week 18 for Cohorts 3A and 3B), it will be considered PD at drug discontinuation visit and counted as PFS event.

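### The PFS-4 evaluable definition in SAP 5.4.2.1 both counts and excludes a subject who dies, or starts new anticancer treatment, before any postbaseline scan (Cohorts 2B and 3B)

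*SAP*

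**What the plan says.** SAP 5.4.2.1 calculates PFS-4 on evaluable subjects, defined by five bullets in each expansion cohort.

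- **Second bullet (2B):** "includes subjects who died or radiologically progressed within 16 weeks after the first administration of study medication". These subjects count as not progression-free, and no scan is required.
- **Third bullet:** a subject who received anticancer treatment in the same window is also included as a failure.
- **Fourth bullet:** "excludes those who discontinue the study due to AE or reasons other than disease progression, death, or receiving anticancer treatment within 16 weeks".
- **Fifth bullet:** "excludes subjects administered any study medication with no baseline or no postbaseline tumor assessments". It makes no exception for death or new treatment.

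Cohort 3B has the same structure with 18 weeks, and its fifth bullet "excludes subjects administered any study medication but had no baseline or no postbaseline tumor assessments".

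Other parts of the SAP bear on the point:

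- **5.1.1** describes evaluable subjects as "those treated at least 4 months or those who died or radiologically progressed within 4 months after first dose", with no scan condition.
- **5.4.2.2, Table 3** treats "Death before first tumor assessment" as a progression event for secondary PFS. The priority text below the table keeps a subject without a postbaseline scan as an event "if the subject died within 125 days in Cohorts 1, 2A and 2B or 97 days in Cohorts 3A and 3B" of first dose, provided no new anticancer treatment was given.
- **5.2.1** requires a baseline and at least one postbaseline tumor assessment for the Per Protocol Analysis Set.
- **8.1** places the first scheduled scan in Week 8 (2B) or Week 6 (3B).

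Protocol 9.7.2 refers to evaluable subjects without defining them.

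**The concern.** PFS-4 is the hypothesis-tested primary endpoint in both osteosarcoma expansion cohorts, and the samples are small: 27 and 15 evaluable subjects. The text puts the same subject inside and outside the denominator, so two programmers following it faithfully could report different primary results. In this open-label study the choice could also be made after the data are known.

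The two readings differ in kind. A death before the first scan is a known failure, not missing information, so removing it can only raise the estimated rate. Running the analysis on both the Full Analysis Set and the Per Protocol Analysis Set gives no protection. The evaluability filter applies to both, and the Per Protocol set imposes the same scan requirement itself.

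**Working it through.** **1. Does the overlap exist?** Take a 2B subject who dies in Week 5 with no postbaseline scan. The second bullet applies (death within 16 weeks), so the subject is an evaluable failure. The fifth bullet applies (dosed, no postbaseline assessment), so the subject is excluded. A subject who starts new anticancer treatment before the first scan meets the third and fifth bullets in the same way. In 3B the result is the same with 18 weeks and a first scan in Week 6. Nothing in 5.4.2.1 ranks the bullets.

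**2. Does another section settle it?** SAP 5.1.1 points to inclusion for deaths but does not mention the fifth bullet. The PFS priority text settles the same clash in favour of counting the death, but for secondary PFS only. Its limits also differ from the PFS-4 windows:

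- 2B: 16 × 7 = 112 days, inside the 125-day limit.
- 3B: 18 × 7 = 126 days, beyond the 97-day limit.

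Even borrowed, that text would not cover the whole 3B window, and it does not cover the new-treatment case.

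**3. The plan's own design figure (SAP 4, 2B).** Continue if at least 5/15; active if at least 10/27. The probability of declaring activity at true rate p is

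Σ (x = 5 to 15) P(X = x | 15, p) × P(Y ≥ max(0, 10 − x) | 12, p).

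This gives 0.0973 at p = 0.25 and 0.8012 at p = 0.45, which agrees with the stated α = 0.1 and power = 80%.

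**4. One unscanned early death, no replacement.** One such subject is an assumption. The one-sided exact p-value is P(X ≥ s | n, 0.25).

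| Cohort | Death counted | Death dropped |
|---|---|---|
| 2B, 10 successes | 10/27: 0.1133 | 10/26: 0.0909 |
| 3B, 7 successes | 7/17: 0.1071 | 7/16: 0.0796 |
| 3B, 7 successes, planned size | 7/16: 0.0796 | 7/15: 0.0566 |

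The first two rows cross 0.10; the third does not. In 2B, 10/27 still meets the two-stage rule, so only the exact test changes.

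**5. Unscanned deaths dropped and replaced.** Let q be the proportion who die before any scan (assumed), and let the true PFS-4 rate in all treated subjects be 25%. Among the subjects kept, the rate becomes 0.25 / (1 − q).

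| q | Rate among kept | 2B rule (5/15, 10/27) | 3B (≥ 7/15) |
|---|---|---|---|
| 0 | 0.2500 | 0.097 | 0.057 |
| 2% | 0.2551 | 0.109 | 0.062 |
| 5% | 0.2632 | 0.128 | 0.072 |
| 10% | 0.2778 | 0.168 | 0.093 |

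In 2B the planned 0.10 is exceeded already at 2%. In 3B the exact test starts well below 0.10 and stays below it over this range.

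**The case against.** The best defence is that the intended reading is reasonably clear. SAP 5.1.1 counts deaths without a scan condition, the PFS rules count an unscanned early death, and the planned Kaplan-Meier 4-month rate would pick up most of these deaths. Such deaths should also be uncommon: eligibility requires a life expectancy of at least 3 months, and scans may be brought forward when clinically indicated. The crossings in the first table occur only at particular counts, and the 2B crossing depends partly on a separate mismatch between the single-stage exact test and the two-stage boundary. All of this stands and limits the size of the problem. It does not remove the contradiction, because none of that text is carried into 5.4.2.1, where the primary denominator is defined. The response-rate rule ("Subjects who do not have a tumor response assessment for any reason will be considered nonresponders and will be included in the denominator") concerns another endpoint, so it is a contrast and not a second contradiction.

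A reader might go further and infer that an event-free subject who stops treatment early but stays in follow-up has an undefined status, so that programmers could also differ there. The documents do not support that. No inclusion bullet admits this subject, and 5.1.1 does not either, so the subject is outside the denominator however the fourth bullet is read. The SAP also uses discontinuing the study to mean stopping study drug: 3.3.4.1 and 13.1 state the same Cycle 1 replacement rule in the two forms. Table 3 likewise censors at treatment discontinuation. Counting a clean post-treatment scan as a success would be a different analysis choice, not another reading of the SAP.

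Nor do the documents show that a 3B subject who stops lenvatinib and completes five chemotherapy cycles can never reach 18 weeks of treatment. Five cycles take 15 weeks on schedule (5 × 21 = 105 days), but the protocol provides for delayed courses and one-week interruptions. Finally, the undefined 4 months in 5.1.1 and 13.2 is not a gap, since 5.4.2.1 states 16 and 18 weeks.

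**Conclusion.** The contradiction is real in both 2B and 3B, for deaths and for new anticancer treatment before any postbaseline scan. It should be fixed before the primary analysis. If the no-scan exclusion governs for deaths, the bias is upward. Its size depends on how many subjects die unscanned, which the documents do not say. One such subject changes the exact-test result only at boundary counts. At assumed rates of 2% to 10% with replacement, the 2B type I error is 0.109 to 0.168 instead of 0.097.

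It would be too strong to say that the SAP will drop these deaths, or that one of them would overturn a cohort's conclusion. The text permits either handling, and most results would not change.

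A minor wording point remains. The fourth bullet should say whether it means stopping study treatment or leaving the study. As written, event-free early stoppers are left out even when a post-treatment Week 16 or Week 18 scan shows no progression.

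**What to change.** In both cohort lists of SAP 5.4.2.1, state that death, radiologic progression or new anticancer treatment within 16 weeks (2B) or 18 weeks (3B) is a failure and stays in the denominator whether or not a postbaseline scan exists. Apply the no-scan exclusion only to subjects with none of these events. Write the rule out in full and do not refer to the PFS priority text, whose limits differ from the PFS-4 windows. Keep the 5/15 and 10/27 boundaries.

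Reword the fourth bullet to say whether it refers to study treatment or study participation. As an option, add a sensitivity analysis on all treated lenvatinib-naïve subjects, classified by their scans, including those after treatment, with unknown status counted as failure. It would show how much the exclusions matter.

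The cost is a sentence or two per cohort, a small change to the derivation and, if the option is taken, one extra table. The reported PFS-4 rate may be lower than it would be with unscanned deaths dropped.

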9.4.8.3 Permitted Concomitant Treatment/Procedures

The following concomitant treatments/procedures are allowed:

- a. Removal of existing (not new) osteosarcoma metastatic lesion (surgical, radiofrequency ablation, etc) as follows:
 - After the completion of first 4 months of the Treatment Period without progression, and
 - Before the first 4 months of the Treatment Period only if there is disease progression assessed by the investigator and the subject will discontinue the study for progression
- b. Palliative radiotherapy in Cohort 2 and 3B is allowed for ≤ 2 significantly symptomatic nontarget lesions. For Cohorts 1 and 3A, it will be allowed after the RD is determined.

If a subject receiving treatment with lenvatinib requires surgery during the study, the stop time and restart time of lenvatinib should be as follows:

- For minor procedures: stop lenvatinib at least 2 days before the procedure and restart it at least 2 days after, once there is evidence of adequate healing and no risk of bleeding.
- For major procedures: stop lenvatinib at least 1 week (5 half-lives) prior to surgery and then restart it at least 1 week after, once there is evidence of adequate healing and no risk of bleeding.

9.4.9 Any additional procedural or patient specific particularities should be discussed with the investigator and the sponsor. Treatment Compliance

Records of treatment compliance for each subject will be kept during the study. Clinical research associates (CRAs) will review treatment compliance during site visits and at the completion of the study.

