- If a subject missed 2 or more tumor assessments before PD or death (No. 9), the subject will be censored on the date of the last adequate tumor assessment before PD or death. Note that if a subject is censored by both this criterion and the anticancer treatment criterion, the earliest censoring date will be used.
- Otherwise, if a subject had an event (No. 3, No. 7, or No. 8), the earliest event date will be used.

2. If a subject did not have PD or death, the censoring date will be the earliest censoring date if the subject met multiple censoring criteria (No. 1, No. 2, No. 4, No. 5, No. 6, No. 9).

Table 4 Censoring Rules for Analysis of Time to Progression

No	Situation	Date of Progression or Censoring	Outcome
1	No baseline tumor assessments	Date of first dose	Censored
2	No postbaseline tumor assessments	Date of first dose	Censored
3	Progression documented between scheduled visits	Date of first radiologic PD assessment	Progressed
4	More than 1 NE tumor timepoint assessment	Date of last adequate radiologic assessment before NE tumor assessments	Censored
5	No progression at time of data cutoff	Date of last adequate radiologic assessment	Censored
6	New anticancer treatment started	Date of last adequate radiologic assessment prior to or on date of new anticancer treatment	Censored
7	Death before first tumor assessment	Date of death	Censored
8	Death between adequate assessment visits*	Date of death	Censored
9	Death or progression after more than one missed visit/tumor assessment**	Date of last adequate radiologic assessment before missed tumor assessments	Censored
10	Treatment discontinuation for reasons other than PD	Date of last radiologic assessment before treatment discontinuation	Censored

CR = complete response, NE = not evaluable, PD = progressive disease, PR = partial response, q6w = every 6 weeks, q8w = every 8 weeks, SD =stable disease.

* Adequate tumor assessment is radiologic assessment at regular interval as defined in the protocol.
** More than 1 missed visit/adequate tumor assessment is defined as having either 1 of the following 2 durations being longer than 18 weeks – 1 day, which is 125 days ($= ((8+1) \times 2 \times 7) - 1$) for subjects on the q8w schedule for tumor assessment in Cohorts 1, 2A, and 2B; while 14 weeks – 1 day, which is 97 days ($= ((6+1) \times 2 \times 7) - 1$) for subjects on the q6w schedule for tumor assessment in Cohorts 3A and 3B:

- a. Duration between two consecutive tumor assessments

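### After a permitted metastasectomy, the PFS and TTP censoring rules keep subjects who later progress and censor those who do not, which generally lowers the secondary Kaplan-Meier curves after month 4

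*SAP*

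**What the plan says.** Protocol 9.4.8.3 allows existing osteosarcoma metastases to be removed "After the completion of first 4 months of the Treatment Period without progression". The SAP (5.4.2.1, paragraph on surgically removed lesions) repeats for Cohorts 2B, 3A and 3B that removal "is permitted after the completion of the first 4 months of the treatment period without PD". It then fixes the status of later scans in a sentence that begins "The time points for tumor response assessment after tumor removal will be considered"; the status it assigns is NE (not evaluable). PD is the only exception, and the SAP introduces it with the words "unless the tumor response is considered PD for the following reasons". Two such reasons are listed: an unequivocal new lesion, and "unequivocal progression of non-target lesions or target lesions".

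The consequence for PFS is in SAP 5.4.2.2. Table 3 row 4 ("More than 1 NE tumor timepoint assessment") censors at the last adequate scan before the NE scans. The priority list under the table decides when each row applies:

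- **Step 1, subjects with PD or death.** It works through rows 1, 2, 6, 10 and 9, then says: "Otherwise, if a subject had an event (No. 3, No. 7, or No. 8), the earliest event date will be used". Row 4 is not named.
- **Step 2, subjects without either.** "If a subject did not have PD or death, the censoring date will be the earliest censoring date if the subject met multiple censoring criteria", and row 4 is among the criteria listed.

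Table 4 and its priority list treat row 4 the same way for TTP. Row 9 in both tables censors an event that comes too long after the last adequate assessment: more than 125 days on the 8-weekly schedule, 97 days on the 6-weekly one. The footnote defines an adequate assessment as a scan at the protocol interval. It does not say whether an NE scan qualifies.

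**The concern.** Read together, these rules make a resected subject's post-surgery time count or not according to what happens in that time. A progressor stays in the risk set and contributes an event. A non-progressor is withdrawn, retrospectively, to the last scan before surgery. That is informative censoring, and it acts on a group selected for being progression-free past 4 months.

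The affected outputs are the PFS and TTP Kaplan-Meier (KM) curves after month 4 and the 12-month rates in the three osteosarcoma cohorts. These cohorts are small (15 to 30 planned in 2B, about 18 lenvatinib-naïve in 3B), so a few resections can move the tail. Because the meaning of adequate is open for NE scans, two programmers could also censor the same subject on different dates.

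**Working it through.** **1. The plan's own windows.** ((8+1) × 2 × 7) − 1 = 125 days and ((6+1) × 2 × 7) − 1 = 97 days. Both reproduce.

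**2. One subject, two outcomes.** A Cohort 2B subject has a clean Week 16 scan, is resected, and is scanned at Weeks 24 and 32.

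- PD at Week 32: step 1 applies. The gap from Week 16 is 16 × 7 = 112 days, under 125, so row 9 does not remove it. Event at Week 32.
- No PD at Week 32: step 2 applies. There are two NE scans, so row 4 censors at Week 16.

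In Cohorts 3A and 3B, with a clean Week 18 scan and PD at Week 30, the gap is 12 × 7 = 84 days, under 97. The contrast is the same.

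**3. Limits of the contrast.** If NE scans are not adequate, PD at Week 40 in 2B is 24 × 7 = 168 days after Week 16. That exceeds 125, so row 9 censors it too, and only about the first two post-surgery scans can yield an event. If NE scans at the regular interval are adequate, row 9 does not bite, but censoring back needs more than one NE scan.

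**4. Direction, by hand (assumed data).** Ten subjects are at risk after month 4 and four are resected. At the first post-surgery scan two of the four have PD. The other two do not, and later have a second scan without PD. The remaining six are progression-free.

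- All follow-up counted: 1 − 2/10 = 0.80.
- SAP rules, with the two resected non-progressors censored back: 1 − 2/8 = 0.75.

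**5. Size, by simulation.** Each scenario used 100,000 subjects, exponential PFS with PFS-4 at the SAP section 4 planning rates, PD detected at the next scheduled scan, surgery uniform between months 4 and 6, and at most 24 months of follow-up. Resection frequency, surgery timing, post-surgery hazard ratio and follow-up are assumptions, because the documents give none of the first three and no maximum follow-up. Errors are in percentage points against counting all post-surgery follow-up.

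Cohort 2B, PFS-4 45%, 30% of progression-free subjects resected (13% of the cohort), hazard ratio 1:

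| Month | All follow-up counted | Error, NE not adequate | Error, NE adequate |
|---|---|---|---|
| 6 | 33.1% | −1.9 | −0.5 |
| 8 | 22.8% | −3.6 | −1.1 |
| 12 | 10.9% | −2.0 | −1.3 |

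Range over 10–50% resected and hazard ratios 0.5–2:

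| Cohort, PFS-4 | Month | NE not adequate | NE adequate |
|---|---|---|---|
| 2B, 45% | 8 | −0.7 to −8.2 | −0.2 to −3.4 |
| 2B, 45% | 12 | 0.0 to −7.5 | −0.1 to −5.0 |
| 3B, 50% | 8 | −0.7 to −7.7 | −0.1 to −3.4 |
| 3B, 50% | 12 | +0.1 to −8.0 | −0.2 to −6.1 |

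The month-4 error was 0.0 in every scenario.

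**6. Does a symmetric rule remove it?** Censoring every resected subject at the last pre-surgery scan differed from full follow-up by at most 0.2 points at months 6, 8 and 12 when surgery was neutral. When surgery changes the hazard the two differ, because censoring at surgery targets progression without surgery.

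**The case against.** The strongest reply is that this touches only untested secondary estimates, usually errs against the drug, and may involve very few subjects. Much of that stands. Removal follows 4 progression-free months, so the tested binomial PFS-4 is essentially untouched. SAP 5.4.2.2 gives the 12-month rate only where enough subjects remain at risk. The cutoff in SAP section 5 is tied to six cycles (Week 24 in 2B, Week 18 in 3A and 3B), so the last enrollees may never accrue two post-surgery scans. Row 10 censors most PD reported after drug discontinuation, so the contrast concerns subjects still on drug.

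It can also be argued that resection is new anticancer treatment under row 6, which would censor both outcomes alike. The text does not favour this: Protocol 9.4.8.3 permits the procedure, and preserving post-surgery PD in SAP 5.4.2.1 would then serve no purpose.

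Four stronger readings are tempting but not supported:

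- **That medians are biased.** Under the planning rates, 25% or 45% are progression-free at month 4 in 2B, and 50% in 3B only at the alternative. The median is normally passed before surgery is allowed.
- **That any later progression counts as an event.** Rows 9 and 10 can remove it.
- **That the loss is around 9 points.** Take 27 subjects with 12 progression-free at Week 16 and six of them resected. Among the unresected, two have PD at Week 24 and one at Week 32; among the resected, two have PD at Week 32; the rest stay progression-free. The SAP rules give 12/27 × 6/8 × 3/6 = 16.7%, against 12/27 × 10/12 × 7/10 = 25.9% with full follow-up. That 9.2-point gap exceeds every simulated scenario and rests on chosen data.
- **That a stable resected subject fails clinical benefit (CBR).** The SAP does not say how the 23-week duration of stable disease is measured or whether an NE scan ends it.

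**Conclusion.** The asymmetry is in the SAP text for both PFS and TTP, and no other rule repairs it. It generally lowers the secondary KM curves after month 4 under either reading of adequate, including the 12-month rates where reported. In the 30%-resected, surgery-neutral Cohort 2B case the error is about −1 to −4 points at month 8 and −1 to −2 at month 12. Across the assumed range it runs from about 0 to −8. It is not uniformly downward: with 10% resected and a post-surgery hazard ratio of 2, one Cohort 3B month-12 scenario showed +0.1. With few resections, or operated subjects who do worse afterwards, it can be negligible at month 12.

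The median is at risk only if more than about half of a cohort is progression-free at the time of surgery. A Cohort 2B subject resected just after month 4 would be censored at Week 16 (day 112), slightly before 4 months (4 × 30.4375 = 121.75 days). That can shrink the KM risk set just before month 4, but it does not alter the binomial endpoint. The rule should be corrected; it does not threaten the primary analysis.

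**What to change.** In SAP 5.4.2.1 and in Tables 3 and 4 with their priority lists, apply one rule to every resected subject regardless of later outcome:

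- **(a)** scheduled post-surgery scans without PD count as adequate, progression-free assessments for PFS and TTP, and stay NE only for CR and PR; or
- **(b)** every resected subject is censored at the last pre-surgery scan, whether or not PD follows.

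Name one as primary and report the other as a sensitivity analysis. Which is primary is the sponsor's choice: (a) includes any surgical effect in the estimate, and (b) discards post-surgery follow-up. State whether an NE scan is adequate for rows 4, 5 and 9. For CBR, state how the duration of stable disease is measured when post-surgery scans are NE.

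The cost is SAP wording and one additional KM run. No new data are needed, since Protocol 9.5.1.3 continues scans on schedule until progression.
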